3.5 Study Groups

This protocol proposes evaluating the healing capacity of eye drops derived from PL of autologous peripheral blood and umbilical cord blood compared with autologous serum. Specifically, three patient groups will be assessed:

Group 1: Patients (n = 34) with diagnosed ocular surface disease receiving PL eye drops from autologous peripheral blood. Recommended dosage: 1–3 drops, four times daily for 4 weeks.

Group 2: Patients (n = 34) with diagnosed ocular surface disease receiving PL eye drops from umbilical cord blood. Recommended dosage: 1–3 drops, four times daily for 4 weeks.

Group 3: Patients (n = 34) with diagnosed ocular surface disease receiving autologous serum eye drops (already used in our clinic). Recommended dosage: 1–3 drops, four times daily for 4 weeks.

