TITLE

Comparative Effects of Autologous Serum, Umbilical Cord Blood-Derived Drops, and Platelet Lysate on Ocular Surface Parameters

Date: October 18 2023

ABSTRACT

Dry eye disease is a multifactorial disorder of the ocular surface that can significantly affect a patient's quality of life. Its treatment depends on the severity of symptoms and usually includes the use of artificial tears or lubricating ointments, while anti-inflammatory eye drops, punctal collagen plugs, or autologous serum drops are used less frequently. Growth factors derived from platelets—either from peripheral blood or umbilical cord blood—such as TGF- β 1, PDGF- $\alpha\alpha/\beta\beta$, FGF-1, and VEGF- α/β , represent new therapeutic approaches that have been successfully applied in regenerative medicine and wound healing.

The aim of this dissertation is to evaluate the application of eye drops derived either from autologous peripheral blood or from umbilical cord blood, and to compare their safety and effectiveness with autologous serum eye drops (three patient groups, age >18 years, diagnosed with ocular surface disease, n = 34).

1.INTRODUCTION

Dry eye disease is a common and multifactorial disorder of the ocular surface that can significantly affect a patient's quality of life due to ocular discomfort and visual disturbances.[1] Its global prevalence ranges from 5% to 50% and increases with age.[2] Patients with dry eye disease can be classified into four categories depending on the severity of their clinical presentation, which may be mild, moderate, severe, or very severe. Dry eye can cause itching, burning, foreign-body sensation, intermittent blurred vision, or even diplopia. The eyes are often red and irritated due to reduced tear production or poor tear quality.[1] Major aggravating factors include eyelid margin inflammation (blepharitis), aging, diet, environmental factors such as air conditioning and low humidity, female sex in association with hormonal changes (pregnancy, menopause), medications (antihistamines, contraceptives), and systemic diseases (rheumatoid arthritis).[3]

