Treatment of dry eye depends on symptom severity and includes artificial tears or lubricating ointments, punctal collagen plugs, anti-inflammatory eye drops, or autologous serum drops. However, surgical intervention may be required to correct eyelid malposition when the eyelid does not close properly ("lagophthalmos").[3] The use of autologous serum was first described in the international literature as a therapeutic option for ocular burns in 1975.[4] The preparation of eye drops for treating dry eye in patients with Sjögren's syndrome was first reported in 1984[5] and remains one of the main therapeutic tools for ocular surface disease.[6] However, autologous serum does not contain platelets, which are rich in important growth factors. Harnessing these growth factors represents one of the most advanced therapeutic approaches for disorders of skin wound healing (e.g., epidermolysis bullosa, diabetic foot, deep dermal burns). [7–11]

For this purpose, modern techniques have been developed to more effectively isolate and deliver platelet-derived growth factors.[12] Blood derivatives rich in growth factors are obtained after centrifugation of whole blood and are classified as:

(a) platelet-rich plasma (PRP), (b) platelet-poor plasma (PPP), (c) platelet lysate (PL), and (d) platelet gel (PG).[13]

In PRP, platelet concentration is 3–5 times higher than normal blood values (peripheral or umbilical cord).[14–15] The release of platelet-derived growth factors occurs either after platelet activation (via exogenous activators such as calcium chloride), which leads to secretion of α -granule contents, or through complete platelet lysis (freeze–thaw cycles).[16] When the latter method is used, the final product is termed PL.

The main biomolecules contained in PL with beneficial effects on tissue regeneration include growth factors such as TGF- β 1, PDGF- $\alpha\alpha/\beta\beta$, FGF-1, VEGF- α/β , HGF, IGF, EGF; anti-inflammatory cytokines such as IL-1ra, IL-10, IL-13; and immunomodulatory elements such as galectins, IDO, NO, HGF, among others.[17] These biomolecules can appropriately activate stem cells, fibroblasts, and progenitor cells to migrate to the site of injury and promote tissue regeneration, as well as regulate inflammatory processes, further supporting tissue repair.[18]

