The use of these products has been applied with remarkable success in extensive lower-limb ulcers in diabetic patients (“diabetic foot”), in patients with second- and third-degree skin burns, and in dystrophic ulcers caused by epidermolysis bullosa.[19–20] The healing outcomes of these wounds are attributed to (1) the rapid release of platelet-derived growth factors (such as TGF- β 1, FGF, VEGF, HGF, PDGF, IGF, etc.), (2) the paracrine action of these factors on various cell populations (epithelial, endothelial, mesenchymal cells and fibroblasts), and (3) the activation of signaling pathways related to cell proliferation, production of structural proteins, and wound healing.[7–8]

In the international literature, the successful use of PL has been described in patients with ocular surface disease, corneal ulcers, and graft-versus-host disease (GVHD).[21][23]

2.AIM

The aim of the present dissertation is to evaluate the application of eye drops derived either from autologous peripheral blood (peripheral blood eye drops – PBED) or from umbilical cord blood (cord blood eye drops – CBED), and to compare their safety and effectiveness with autologous serum eye drops in patients with ocular surface disease.

It has been reported in the literature that umbilical cord blood may contain a greater number of immunomodulatory components compared to peripheral blood, due to circulating biomolecules such as HLA-G. [17] These biomolecules are responsible for maternal tolerance toward the semi-allogeneic fetus. Additionally, patients with cardiac or metabolic diseases, or those receiving treatments that affect platelet levels, produce PL of reduced quality with respect to its biomolecular content. For such patients, the use of blood-derived products of allogeneic origin may represent the best possible option.

It is particularly noteworthy that PL production is achieved through simple centrifugation and freeze–thaw cycles, and is therefore classified as a minimally manipulated product according to paragraph 21 CFR of the FDA.[22] Consequently, its production and administration do not fall under the category of pharmaceutical products and thus do not require special authorization from the National Organization for Medicines (EOF) for broad clinical study.

3.METHODS

In this prospective randomized study, eye drops will be prepared and administered using either autologous peripheral blood from the patients or umbilical cord blood.

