3.6 Evaluation of Eye Drop Application

The effectiveness of the therapeutic interventions will be assessed using specialized ophthalmic techniques. Epithelialization time is defined as the interval from treatment initiation to complete epithelial healing.

For qualitative assessment of tear film stability, the tear breakup time (TBUT) will be measured—the interval between the last blink and the appearance of the first dry spot after instillation of 2% fluorescein. A TBUT < 5 seconds is indicative of ocular surface disease.

For quantitative assessment of tear production, the Schirmer test will be used, measuring the wetting length of a 5 mm × 35 mm filter paper strip (No. 41 Whatman). The strip is placed at the junction of the middle and outer third of the lower eyelid, and the patient closes their eyes for 5 minutes. The test may be performed without anesthesia (Schirmer I) or with anesthesia (Schirmer II). Wetting < 10 mm (Schirmer I) or < 6 mm (Schirmer II) is considered abnormal.

Corneal epithelial damage will be assessed using fluorescein staining. Tear meniscus height—and thus tear volume—will also be measured.

To evaluate subjective symptoms, each patient will complete the Ocular Surface Disease Index (OSDI) questionnaire, consisting of 12 questions assessing symptoms and their impact on daily life. It includes three subcategories 1) ocular symptoms, 2) vision-related daily functioning, 3) environmental triggers. Responses range from 0 (“none of the time”) to 4 (“all of the time”). Total scores range from 0–100: 0–12 = normal, 13–22 = mild disease, 23–32 = moderate disease, 33 = severe ocular surface disease.[27]

Inclusion Criteria

- Age > 18 years
- Ocular surface disease due to chronic blepharitis
- Ocular surface disease due to Sjögren’s syndrome
- Toxic keratopathy from antiglaucoma drops
- Persistent epithelial defect after ocular surgery (e.g., keratoplasty)
- Chemical burn
- Post-herpetic keratitis

Exclusion Criteria

- Age < 18 years
- Active infectious disease

4.DISCUSSION

In the present doctoral dissertation, a comparative study will be conducted for the first time in the international literature using eye drops derived from autologous peripheral blood or umbilical cord blood in patients with ocular surface disease.

The expected outcomes of this study include healing of the injured eye and an increase in the number of epithelial cells within a shorter period of time in patients belonging to Groups 1, 2 and 3.

5.BIBLIOGRAPHY

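### Eligibility does not exclude, record or stratify by current or recent autologous serum use, although serum is the comparator and the clinic already uses it

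*Combined protocol and SAP*

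**What the plan says.** The Methods open by calling the trial randomised: "In this prospective randomized study, eye drops will be prepared and administered using either autologous peripheral blood from the patients or umbilical cord blood". Section 3.5 sets three groups of 34. Groups 1 and 2 receive platelet lysate (PL) from peripheral or cord blood, and Group 3 consists of patients "receiving autologous serum eye drops (already used in our clinic". All are treated for 4 weeks. The Introduction says that serum "remains one of the main therapeutic tools for ocular surface disease".

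Eligibility is listed at the end of 3.6. The inclusion criteria name adults with one of several causes of ocular surface disease, among them Sjögren's syndrome, chemical burn and "Persistent epithelial defect after ocular surgery (e.g., keratoplasty". There are two exclusions: age under 18 and "Active infectious disease". Neither concerns earlier treatment, and no run-in or treatment-free baseline is described.

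Section 3.4 lists one-way ANOVA, Kruskal-Wallis, Mann-Whitney and Wilcoxon tests at the 0.05 level. It mentions no adjustment for baseline or treatment history. Section 3.6 counts epithelialization time from the start of treatment.

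**The concern.** The aim in section 2 is to compare both PL products with autologous serum. A patient who is on serum drops and still symptomatic meets every criterion as written. In Group 3 that patient carries on with the same product; in Groups 1 and 2 the same patient changes to a different one. Either way, the baseline TBUT, Schirmer, staining and OSDI values are values on serum.

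Three things follow.

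- A before-after change measured from an on-serum baseline does not describe the effect of starting the assigned product.
- For a Group 3 patient already on serum, the start of treatment is ambiguous: it could be the first serum course or the day of randomisation.
- The comparison with serum mixes first use with re-treatment versus switching, in proportions nobody will know unless prior use is recorded.

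Prior users are plausible entrants. The clinic already supplies the product, and the Introduction traces serum to ocular burns and Sjögren's syndrome, both of which are entry diagnoses here.

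**Working it through.** **Inputs from the documents.** 34 per group (3.5), hence 3 × 34 = 102 in total; significance level 0.05 (3.4). The abstract gives "three patient groups, age >18 years, diagnosed with ocular surface disease, n = 34" without saying whether that is per group; I follow 3.5. The figure of 34 cannot be reproduced, because 3.4 states no effect size, SD or power.

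**Inputs assumed, not in the documents.** The share p of each arm that are prior serum users; a gain of 15 OSDI points on any product in first-time users; SD 20; zero gain from more serum in prior users; a gain of 7.5 to 15 points for them on switching to PL.

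**Step 1: does Group 3 receive more prior users than the other groups?** Under 34:34:34 allocation the number in any one arm is hypergeometric.

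| Prior users among 102 | Expected per arm | 95% range |
|---|---|---|
| 10 | 3.3 | 1–6 |
| 26 | 8.7 | 5–13 |
| 51 | 17.0 | 12–22 |

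The expectation is the same in every arm.

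**Step 2: does an on-serum baseline alone favour an arm?** Suppose the products are equal and a share q of each arm enters already improved by 0.8 SD. Mean change is then (1 − q) × 0.8, which is 0.80, 0.60 and 0.40 SD at q = 0, 0.25 and 0.50. A simulation gave these means in both arms, a difference between arms of about 0, and rejection of about 5%. Carry-over alone dilutes within-group change and leaves the comparison between arms alone.

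**Step 3: what if the prior users are inadequate responders?** Take the products as equal in first-time users. The gain in Group 3 is 15 × (1 − p). The gain in a PL group is 15 × (1 − p) + p × s, where s is the gain on switching. The spurious difference is therefore p × s, with s from 7.5 to 15. Its standard error is 20 × √(2/34) = 4.85. Two-sided t-test rejection uses the noncentral t with 66 df and noncentrality p × s / 4.85.

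| p | Group 3 gain | PL gain | Difference | Noncentrality | Rejection |
|---|---|---|---|---|---|
| 0 | 15 | 15 | 0 | 0 | 5% |
| 10% | 13.5 | 14.25–15 | 0.75–1.5 | 0.15–0.31 | 5.3–6.1% |
| 30% | 10.5 | 12.75–15 | 2.25–4.5 | 0.46–0.93 | 7.4–15.0% |
| 50% | 7.5 | 11.25–15 | 3.75–7.5 | 0.77–1.55 | 11.9–33.2% |

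The t-test is not in 3.4, so I repeated this with the planned one-way ANOVA: both PL arms shifted by δ, noncentrality 34 × (2/3) × δ² / 400, on 2 and 99 df. Rejection is 5.2–5.9%, about 7–14% and about 11–33% at the same shares.

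**Step 4: sensitivity to the zero-gain assumption.** In SD units, let the first-use response be 0.8 SD, with full response to PL in prior users. If they gain nothing from more serum, the shift is q × 0.8 = 0.08, 0.20 and 0.40 SD at q = 0.10, 0.25 and 0.50, and rejection is 6.3%, 13.1% and 37.8% (normal approximation). If they keep half the serum response, the shift halves and rejection is 5.3%, 7.0% and 13.1%.

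**The case against.** The trial is randomised, so the arms are comparable whatever the treatment history, and including previously treated patients is a legitimate real-world question. It changes the population described, not the comparability of the groups. This stands, and it rules out two readings a reader might infer. One is that Group 3 collects patients who have failed serum: nothing ties history to assignment, and Step 1 shows equal expected shares. The other is that an on-serum baseline by itself tilts the comparison against serum, which Step 2 contradicts.

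The quoted parenthesis in 3.5 describes the product, not the patients. That also stands: it does not say that anyone entering the trial has used serum, and the gap rests on the criteria in 3.6. The abstract moreover lists serum drops among the treatments given less often than lubricants, which points towards a small share of prior users; at 10% the effect on error is barely visible.

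The inputs to Step 3 are all assumed, and OSDI is not named as the primary outcome. Lapsed users might respond again to serum, and recent starters might still be improving. If patients known to respond to or tolerate serum were the ones who entered, the shift could go the other way.

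What the objection does not answer is that equal shares do not mean equal effects: only one arm repeats a product these patients have already had. Nor could the planned tests separate the two situations, and if history is not collected no later analysis can.

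**Conclusion.** The gap holds as a design weakness that is cheap to close. Under the plan as written, a current serum user can be randomised to continue the comparator or to switch from it, with an on-treatment baseline and, in Group 3, no clear start for epithelialization time. Dilution of within-group change follows whenever such patients have already benefited from serum or gain little from more of it.

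A bias against serum between arms is conditional. It needs an appreciable share of prior users who do worse on more serum than on PL. On the assumptions shown, with truly equal products, it ranges from negligible at a 10% share to 3.75–7.5 OSDI points at 50%. The documents supply neither the share nor the response, so the actual size is unknown and the direction is not certain. A reader might conclude that the comparison is biased against serum; the documents support only that it could be, and that the plan has no means of telling.

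**What to change.** In the exclusion criteria of 3.6, add current use of any blood-derived eye drops at baseline, or use within a fixed period before it. The investigators should set that period, and no patient should be taken off treatment in order to enrol. Cost: one eligibility line, slightly slower recruitment and a narrower population.

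If recruitment does not allow this:

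- record prior serum use (yes/no) at entry and stratify randomisation by it;
- in 3.4, adjust the comparison between arms for it, for example with a linear model containing arm, prior use and the baseline value;
- state in 3.6 from which date epithelialization time runs for a patient already on the assigned product;
- report the no-prior-use subgroup as a sensitivity analysis.

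Adjustment balances the arms and sharpens the estimate, but it does not remove a difference between re-treating and switching; the subgroup result is what would reveal one. It should not become the sole primary comparison, because that would cut into 34 per arm: at a 30% share about 34 × 0.7 ≈ 24 would remain. Cost: one stratum, one history field and one added model.

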3.6 Evaluation of Eye Drop Application

The effectiveness of the therapeutic interventions will be assessed using specialized ophthalmic techniques. Epithelialization time is defined as the interval from treatment initiation to complete epithelial healing.

For qualitative assessment of tear film stability, the tear breakup time (TBUT) will be measured—the interval between the last blink and the appearance of the first dry spot after instillation of 2% fluorescein. A TBUT < 5 seconds is indicative of ocular surface disease.

For quantitative assessment of tear production, the Schirmer test will be used, measuring the wetting length of a 5 mm × 35 mm filter paper strip (No. 41 Whatman). The strip is placed at the junction of the middle and outer third of the lower eyelid, and the patient closes their eyes for 5 minutes. The test may be performed without anesthesia (Schirmer I) or with anesthesia (Schirmer II). Wetting < 10 mm (Schirmer I) or < 6 mm (Schirmer II) is considered abnormal.

Corneal epithelial damage will be assessed using fluorescein staining. Tear meniscus height—and thus tear volume—will also be measured.

To evaluate subjective symptoms, each patient will complete the Ocular Surface Disease Index (OSDI) questionnaire, consisting of 12 questions assessing symptoms and their impact on daily life. It includes three subcategories 1) ocular symptoms, 2) vision-related daily functioning, 3) environmental triggers. Responses range from 0 (“none of the time”) to 4 (“all of the time”). Total scores range from 0–100: 0–12 = normal, 13–22 = mild disease, 23–32 = moderate disease, 33 = severe ocular surface disease.[27]

Inclusion Criteria

- Age > 18 years
- Ocular surface disease due to chronic blepharitis
- Ocular surface disease due to Sjögren’s syndrome
- Toxic keratopathy from antiglaucoma drops
- Persistent epithelial defect after ocular surgery (e.g., keratoplasty)
- Chemical burn
- Post-herpetic keratitis

Exclusion Criteria

- Age < 18 years
- Active infectious disease

4.DISCUSSION

In the present doctoral dissertation, a comparative study will be conducted for the first time in the international literature using eye drops derived from autologous peripheral blood or umbilical cord blood in patients with ocular surface disease.

The expected outcomes of this study include healing of the injured eye and an increase in the number of epithelial cells within a shorter period of time in patients belonging to Groups 1, 2 and 3.

5.BIBLIOGRAPHY

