3.4 Statistical Power Analysis (G-Power Analysis) and Data Evaluation

Data analysis for all study parameters will be performed using GraphPad Prism v6.01 (GraphPad Software, San Diego, CA, USA). Parameter analysis will include one-way ANOVA, non-parametric Kruskal Wallis, Mann-Whitney and Wilcoxon tests.. Statistical significance is set at $p < 0.05$.

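### Epithelialization time is a time-to-event outcome, but the plan gives it no analysis set, no rule for unhealed eyes and no time-to-event method

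*Combined protocol and SAP*

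**What the plan says.** - **Outcome.** Section 3.6 (Evaluation of Eye Drop Application) lists it first: "Epithelialization time is defined as the interval from treatment initiation to complete epithelial healing". It does not say what is recorded for an eye that has not healed, or for one with nothing to heal.
- **Tests.** Section 3.4 says: "Parameter analysis will include one-way ANOVA, non-parametric Kruskal Wallis, Mann-Whitney and Wilcoxon tests". The sentence before it concerns software: "Data analysis for all study parameters will be performed using GraphPad Prism v6.01". No test is assigned to any particular outcome. Kaplan-Meier, log-rank, Cox and censoring are not mentioned anywhere.
- **Population.** The inclusion criteria under Section 3.6 admit, among others, "Ocular surface disease due to chronic blepharitis" and "Ocular surface disease due to Sjögren’s syndrome", with no requirement for an epithelial defect. One criterion, for patients after eye surgery, names a defect. The expected share of patients with a defect is not given.
- **Time horizon.** Section 3.5 gives the same course for each of the three groups of 34: "Recommended dosage: 1–3 drops, four times daily for 4 weeks". This is the length of treatment. Neither the end of follow-up nor a visit schedule is stated.

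**The concern.** The outcome is an interval that ends in an event. Two kinds of patient have no value: those whose defect is still open at the last examination, and those who had no defect. ANOVA needs a number from everyone it includes, so these patients must be left out or given a value, and the plan leaves that choice open until the data are in.

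Leaving out unhealed eyes removes the treatment failures, and more of them from the slower arm. The arms then look alike, and a product that heals few eyes, but heals those quickly, can look good. Scoring eyes without a defect as zero would tie an arm's mean to its case mix. Section 3.5 presents the trial as a comparison of healing capacity, so this outcome bears directly on the question asked.

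**Working it through.** **The plan's own figure.** There is none for this endpoint. Section 3.4 is titled as a power analysis but gives only the 0.05 level, so 34 per arm cannot be reproduced. For two means at 80% power it corresponds to a standardized difference of (1.960 + 0.842) × √(2/34) = 0.68, which says nothing about healing times.

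**Inputs from the documents.** 34 patients per arm (Section 3.5); significance level 0.05 (Section 3.4).

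**Assumptions.** The documents give none of the following: exponential healing times; one eye per patient; two-sided tests; two arms compared; every eye observed to day 28, with the healing date known exactly. Day 28 is borrowed from the treatment course.

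**Step 1: means.** With median m, h = ln 2 / m and S = exp(−28h), the share unhealed at day 28:
- true mean = 1/h
- mean among healed eyes = 1/h − 28S/(1 − S)
- mean with unhealed eyes set to 28 days = (1 − S)/h

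For m = 14: S = 0.25, and the healed-only mean is 20.20 − 28 × 0.25/0.75 = 10.86. For m = 28: S = 0.50, and it is 40.40 − 28 × 0.50/0.50 = 12.40.

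| Median (days) | Unhealed at day 28 | True mean | Healed only | Unhealed set to 28 |
|---|---|---|---|---|
| 3 | 0.2% | 4.33 | 4.28 | 4.32 |
| 6 | 3.9% | 8.66 | 7.51 | 8.32 |
| 7 | 6% | 10.10 | 8.23 | 9.47 |
| 14 | 25% | 20.20 | 10.86 | 15.15 |
| 28 | 50% | 40.40 | 12.40 | 20.20 |

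Differences between arms, from the table:
- 14 vs 28 days: true 20.20; healed only 1.54; set to 28, 5.05.
- 7 vs 14 days: true 10.10; healed only 2.63; set to 28, 5.68.
- 3 vs 6 days: true 4.33; healed only 3.23; set to 28, 4.00.

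**Step 2: power, by simulation.**

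| Medians, defect eyes per arm | Mann-Whitney, healed only | Mann-Whitney, unhealed tied at 28 | Log-rank |
|---|---|---|---|
| 14 vs 28, n = 34 | about 10% | about 55% | about 60% |
| 7 vs 14, n = 34 | about 23% | about 66% | about 75% |

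Repeat runs agreed to within two or three percentage points. With no true difference, all the tests rejected in about 5% of trials.

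**Step 3: closed-form check of log-rank.** The healing-rate ratio is 2, and power = Φ(√D × ln 2 / 2 − 1.96), where D is the expected number of healed eyes in the two arms.
- 14 vs 28, n = 34: D = 34 × (0.75 + 0.50) = 42.5; Φ(2.26 − 1.96) = 62%.
- 7 vs 14, n = 34: D = 34 × (0.9375 + 0.75) = 57.4; Φ(2.63 − 1.96) = 75%.
- 14 vs 28, n = 17 (half the patients have a defect): D = 21.25; Φ(1.60 − 1.96) = 36%.

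**Step 4: eyes without a defect.** Suppose they were scored as zero, healing truly averaged 14 days in both arms, and 40% vs 60% had a defect. The arm means would be 14 × 0.40 = 5.6 and 14 × 0.60 = 8.4 days, a spurious gap of 2.8 days.

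**The case against.** Several objections stand and limit the point.

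- **No test is tied to this outcome.** A reader might infer that the plan prescribes ANOVA or rank tests for epithelialization time. It does not: the phrase that covers every parameter belongs to the software sentence, and the list of tests is open-ended. The fault is a missing method, with only unsuitable or incomplete ones on offer.
- **Censoring at four weeks is not stated.** Four weeks is the treatment course. Every figure above depends on the assumed day-28 cut-off. Any finite follow-up raises the same problem, but its size would differ.
- **Rank tests are not wrong in themselves.** They need only an ordering. With a common cut-off and unhealed eyes placed last, Mann-Whitney holds its error rate and loses little against log-rank (about 55% vs 60%). What it lacks is an estimate of healing speed, and the plan does not state that ranking rule.
- **Setting unhealed eyes to 28 days has a meaning.** With complete follow-up it compares mean time unhealed within 28 days. That is a legitimate quantity, but smaller than the difference in healing time.
- **Leaving out patients without a defect is right for this endpoint.** Scoring them zero would do harm, but the plan nowhere proposes it.
- **No primary outcome is named.** The Discussion expects faster healing in all three groups, which is not a claim about differences between arms. A reader might treat this as the trial's decisive endpoint, but the documents do not say so.

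None of this supplies a rule for unhealed eyes, an analysis set or a way to estimate healing speed.

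**Conclusion.** The concern holds as a gap in the plan that should be fixed. It is not shown to invalidate the trial, since no primary outcome is named.

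ANOVA, or any test confined to healed eyes, may understate differences in healing speed. Under the stated assumptions, a true difference of 20.2 days shrinks to about 1.5 days among healed eyes, and power is about 10% rather than 60%. With faster healing (7 vs 14 days), 10.1 days shrinks to about 2.6, and power is about 23% rather than 75%.

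A reader might go further and conclude that healing speed will be misestimated. The documents do not support that. The size depends on the share unhealed and on a handling rule, and neither is given. If nearly all eyes heal in both arms the bias is small: at a median of 3 days, with 0.2% unhealed, the healed-only mean is 4.28 against a true 4.33.

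**What to change.** In Section 3.6:
1. Define epithelialization time only for eyes with an epithelial defect at baseline.
2. State the end of follow-up and the examination times used for this endpoint. Without them, censoring cannot be defined.

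In Section 3.4:

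3. Analyse it with Kaplan-Meier curves and a log-rank test, and report a hazard ratio for healing with its 95% CI. Censor unhealed eyes at their last examination. If healing is seen only at visits, use an interval-censored method.
4. Report the proportion healed at week 4 by arm, with the difference and its 95% CI.
5. Remove this outcome from ANOVA.

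The cost is a few sentences, best written before any outcome data are seen. The downside is that fewer than 34 patients per arm will contribute, so precision is lower: if half have a defect (17 per arm), log-rank power at 14 vs 28 days is about 36%. The plan should say so. Patients without a defect carry no information on healing time under any method.
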